12.2.1.2. Serious Adverse Event (SAE)

A serious adverse event is an AE occurring during any study phase (i.e., baseline, treatment, washout, or follow-up), and at any dose of the investigational product, comparator, or placebo, that fulfills one or more of the following:

- Results in death.
- It is immediately life-threatening.
- It requires in-subject hospitalization or prolongation of existing hospitalization.
- It results in persistent or significant disability or incapacity.
- Results in a congenital abnormality or birth defect
- It is an important medical event that may jeopardize the subject or may require medical intervention to prevent one of the outcomes listed above.

All SAEs that occur after any subject/subject h s been enrolled, before treatment, during treatment, or within 30 days following the cessation of treatment, whether they are related to the study, must be recorded on forms provided by the Sponsor or its representatives.

12.2.1.3. Other Adverse Event (OAE)

OAEs will be identified by the Drug Safety Physician and if applicable also by the Clinical Study Team Physician during the eval ation of safety data for the Clinical Study Report. Significant adverse events of clinical importance, other than SAEs and those AEs leading to discontinuation of the subject/subject from the study, will be classified as OAEs. For each OAE, a narrative may be written and included in the Clinical Study Report. Adverse events of special interest (AESI) to characterize ecopipam are programmatically listed for review and will be identified by the Medical Director(s) and Drug Safety Physician. The AEs include weight gain, extra-pyramidal reactions and suicidal ideations and behavior.

12.3. Relationship to Study Drug

An Investigator who is qualified in medicine must make the determination of relationship to the investigational product for each AE (Unrelated, Possibly Related or Probably Related). The Investigator should decide whether, in his or her medical judgment, there is a reasonable possibility that the event may have been caused by the investigational product. If no valid reason exists for suggesting a relationship, then the AE should be classified as "unrelated". If there is any valid reason, even if undetermined, for suspecting a possible cause-and-effect relationship between the investigational product and the occurrence of the AE, then the AE should be considered "related."

Protocol EBS-101-TD-301 Version 9.0, 05 March 2024

If the relationship between the AE/SAE and the investigational product is determined to be "possible" or "probable" the event will be considered related to the Investigational Product for the purposes of expedited regulatory reporting.

12.4. Recording Adverse Events

Adverse events spontaneously reported by the subject and/or in response to an open question from the study personnel or revealed by observation will be recorded during the study at the investigational site. Clinically significant changes in laboratory values, blood pressure, and pulse can be reported as AEs per the investigator's judgement. However, abnormal values that constitute an SAE or lead to discontinuation of administration of study drug must be reported and recorded as an AE. Information about AEs will be collected from the signing of consent form until the end of the study. SAE information will be collected from signing of consent form until 30 days following the last dose of study drug. The AE term should be reported in standard medical terminology when possible. For each AE, the investigator will evaluate and report the onset (date and time), resolution (date and time), intensity, causality, action taken, serious outcome (if applicable), and whether it caused the subject to discontinue the study.

Intensity will be assessed according to the following scale:

- Mild (awareness of sign or symptom, but easily tolerated)
- Moderate (discomfort sufficient to cause interference with normal activities)
- Severe (incapacitating, with inability to perform normal activities)

It is important to distinguish between serious and severe AEs. Severity is a measure of intensity whereas seriousness is defined by the criteria under Section 12.2.1.2. An AE of severe intensity may not be considered serious.

Should a pregnancy of a subject or partner occur, it must be reported and recorded on Sponsor's or Sponsor approved pregnancy form. Pregnancy is not regarded as an AE unless there is a suspicion that an investigational product may have interfered with the effectiveness of a contraceptive medication. Reports of pregnancy must be submitted without undue delay and no longer than 24 hours of awareness of the event:

Email Address: [contact]

Fax no. Americas: [contact]

Fax no. Europe and ROW [name]

The outcome of all pregnancies (spontaneous miscarriage, elective termination, normal birth, or congenital abnormality) must be followed up and documented even if the subject was discontinued from the study.

All reports of congenital abnormalities/birth defects are SAEs. Spontaneous miscarriages should also be reported and handled as SAEs. Elective abortions without complications should not be handled as AEs.

12.5. Reporting Serious Adverse Events

All SAEs (related and unrelated) will be recorded from the signing of consent form until 30 days following the end of treatment exposure. Any SAE considered possibly or probably related to

Protocol EBS-101-TD-301 Version 9.0, 05 March 2024

the investigational product and discovered by the Investigator at any time after the study should be reported. All SAEs must be reported without undue delay and no longer than 24 hours of awareness of the event:

Email Address: [contact]

Fax no. USA: [contact]

Fax no. outside USA [name]

The Investigator must complete, sign and date the SAE pages, verify the accuracy of the information recorded on the SAE pages with the corresponding source documents, and send a copy to the Sponsor or its representatives.

Additional follow-up information, if required or available, should all be sent to the Sponsor or its representatives without undue delay and no longer than 24 hours of awareness of the event and this should be completed on a follow-up SAE form and placed with the original SAE information and kept with the appropriate section of the CRF and/or study file.

The Sponsor and its representatives are responsible for notifying the relevant regulatory authorities of certain events. It is the Principal Investigator's responsibility to notify the IRB or IEC of all SAEs that occur at his or her site. Investigators will also be notified of all unexpected, serious, drug-related events (7/15 Day Safety Reports) that occur during the clinical study. Each site is responsible for notifying its IRB or IEC of these additional SAEs.

Protocol EBS-101-TD-301 Version 9.0, 05 March 2024

13. STATISTICS

All data analyses will be performed by the Sponsor or its representatives after the study is completed, and the database is finalized and released. The statistical analyses described in this section will be performed using SAS 9.4. All collected data will be listed. Additional analyses may need to be conducted for data not collected at sites and/or via remote administration due to restrictions because of the COVID-19 pandemic or other qualifying event, details of these additional analyses will be specified in the SAP.

13.1. Analysis Population

The Modified Intention-to-Treat (mITT) population will include all randomized subjects who received at least one dose of study drug post randomization. The mITT population will be used for the analysis of primary, secondary and exploratory efficacy endpoints. All analyses performed for the mITT population will also be performed for the Intent-to-Treat (ITT) population defined as all randomized subjects.

The Per-Protocol (PP) population will include subjects from the mITT population who have no major protocol deviations that may adversely impact assessment of efficacy. Before data are released for statistical analysis, a blinded review of all data will be performed by the Sponsor's clinical team to identify protocol deviations that may potentially affect the results. At this time, it will be determined if subjects and/or data should be excluded from the PP Population. The list of subjects or observations to be excluded from the PP Population, along with the reason for exclusion, will be finalized prior to database unblinding. Protocol deviations that occur due to COVID-19 related issues or other qualifying vents will be categorized separately as applicable.

The Safety population will include all subjects who received at least one dose of study drug. The safety population will be used for the analysis of the safety endpoints.

The Pharmacokinetics (PK) population will include all subjects from safety population who have a valid concentration measurem nt

13.2. Data Safety Monitoring Board

An independent data safety and monitoring board (DSMB) consisting of a physician experienced in the conduct of clinical studies (Chairman with TD experience), one clinician and one statistician experienced in TD will review the data at the interim analysis. The data will be cleaned by the data management group, and the analysis and reporting of the interim data to the DSMB will be the responsibility of an independent statistical group (which will not be directly involved in the conduct of the study). The DSMB will meet after the data presentation and issue recommendations. Minutes of the DSMB will be submitted to the sponsor after the study has been unblinded and will be appended to the final study report.

Full details of the DSMB procedures including primary responsibilities of the DSMB, its relationship with other study components, its membership, and the purpose and timings of its meetings will be documented in a DSMB charter. These details will also include procedures to ensure confidentiality and proper communication, the guidelines to be implemented by the DSMB and an outline of the content of the closed reports (unblinded) and open reports (blinded) that will be provided to the DSMB.

Protocol EBS-101-TD-301 Version 9.0, 05 March 2024

13.3. Interim Analysis

An interim analysis (IA) will be conducted by an independent data safety monitoring board (DSMB) after approximately 70% of Relapse events have accrued (34 Relapse events). The 2-sided alpha level for the IA is 0.005. If statistical significance is reached at the IA, the DSMB can recommend stopping the study for overwhelming efficacy. If the study proceeds to the planned completion, the final 2-sided alpha level will be 0.0492. In addition to the possibility of stopping early for efficacy, a conditional power analysis will be performed to assess whether the total number of relapse events should be increased beyond 49 in order to increase statistical power at the final analysis. If the probability based on conditional power of a successful study is too small and does meet pre-specified criteria, the DSMB can recommend stopping the study for futility. If the probability of a successful study is reasonable, the DSMB can recommend continuing the trial as planned or can also recommend continuation of the trial with a sample size adjustment based on conditional power. Interpretation of conditional power will be guided by the promising zone approach. ³² One consequence of this approach is that no adjustment of the final alpha level will be required (other than the alpha spending of the IA). Full details will be provided in the Statistical Analysis Plan (SAP).

13.4. Planned Analysis

13.4.1. Efficacy Analysis

The primary efficacy endpoint is time from Randomization to Relapse defined as a loss of $\geq 50\%$ of the improvement experienced on the YGTSS-TTS at the last visit in the open-label Stabilization period (Week 12), or initiation of additional medications to treat symptoms of TD, or requirement of hospitalization for w rsening symptoms of TD in subjects ≥ 6 and < 18 years during the double-blind R/WD period for ecopipam compared to placebo. Data from subjects who complete or discontinue from the double-blind R/WD period without Relapse will be considered as censored obs rvations. The log rank test will be the primary test of statistical significance. Kaplan-Meier curves will be used to compare the times to relapse between the treatment groups. The hazard ratio and its 95% confidence interval (CI) will be estimated from the Cox proportional hazard model with treatment as a factor. The proportional hazards assumption will be evaluated graphically and analytically, for example by assessing martingale and Schoenfeld residuals and by modeling time-dependent covariates. The analysis of the primary efficacy endpoint will be performed in the mITT and PP populations according to the randomized treatment. Details will be provided in the Statistical Analysis Plan.

The time-to-event secondary and exploratory endpoints related to Relapse will be analyzed in a similar manner as the primary endpoint. The exploratory endpoints of mean change will be assessed with a Mixed Model for Repeated Measures (MMRM) model using the SAS MIXED procedure, with a REPEATED statement, with no imputation. The model will include fixed effects for treatment, visit, the interaction between treatment and visit, and a covariate for baseline score for the given assessment and other covariates such as gender, age group, race/ethnicity, and region. All secondary and exploratory endpoints will be analyzed in the mITT population according to randomized treatment. Details will be provided in the Statistical Analysis Plan.

Protocol EBS-101-TD-301 Version 9.0, 05 March 2024

The CGI-TS-S endpoints currently listed as time-to-event exploratory endpoints may be considered as secondary endpoints, if there is a strong correlation between subjects meeting Relapse criteria based on YGTSS-TTS and those who also had at least a 1-point reduction on CGI-TS-S. The strong correlation would suggest Relapse is not a competing risk. Details will be provided in the Statistical Analysis Plan.

The time-to-event estimand for the primary endpoint, which uses the mITT study population, and for the time-to-event secondary and exploratory endpoints related to Relapse will rely on a treatment policy strategy (which also has elements of a composite strategy, in that three intercurrent events, initiation of additional medications and hospitalization for worsening symptoms are incorporated as part of the definition of the primary endpoint). The intercurrent events of loss to follow-up will be assumed unrelated to treatment and treated in estimation as censored observations. Sensitivity analyses for the primary endpoint may assess alternate treatment of such missing data; details will be provided in the Statistical Analysis Plan.

The time-to-event endpoints not related to Relapse will rely on a treatment policy strategy. A cumulative incidence approach will be used to account for the competing risk of study discontinuation due to Relapse. Cause-specific Cox models will be used to obtain the hazard ratio and its 95% CI for time to worsening. In this model, subjects who complete or discontinue from the double-blind randomized withdrawal period before meeting endpoint criteria and for reasons not related to Relapse will be censored at the time of discontinuation. In addition, we will consider graphical and descriptive approaches in correlating the YGTSS with other scores (e.g., CGI-TS-S) in the study subjects across time points.

For exploratory endpoints of mean change, the difference in means between treatment arms in change from Randomization (Week 12) to Week 24 or from Baseline (Day 1) to Week 24, a sensitivity analysis may be performed. For the intercurrent events of study treatment discontinuation due to lack of efficacy, treatment related adverse events, death prior to Week 24 and Relapse for subjects with no assessment at Week 24, the non-collected data of assessment at Week 24 will be multiple imput d using similar subjects (relevant demographic/baseline characteristics) from the placebo arm. For exploratory endpoints of mean change to fixed time point, additional analyses will be performed by time point.

In consideration of missing data, additional multiple imputation or tipping point methods may be used as a sensitivity analysis, such as:

- Missing at Random (MAR) predictive mean matching multiple imputation method
- Missing not at Random (MNAR) "jump to reference" multiple imputation method
- Tipping point analysis under MNAR assumption
- The mean change from Baseline (Day 1) to Week 12 (open-label) in YGTSS-TTS will be calculated. The paired t-test will be used for analyzing the change from baseline within treatment.
- The percentage of subjects with a 25% or greater decrease in their YGTSS-TS will be analyzed using Fisher Exact test.
- A fixed-sequence statistical strategy will be used to test selected efficacy endpoints in a predefined rank order hierarchy which will be outlined in the SAP.

Protocol EBS-101-TD-301 Version 9.0, 05 March 2024

The full details will be specified in the SAP.

Subgroup analyses will be conducted on all efficacy endpoints for the following populations:

- Children (≥ 6 and < 12 years of age), Adolescents (≥ 12 and < 18 years of age), and Adults (≥ 18 years of age).
- Subjects per region
- Males and Females
- Ethnicity and Race

Additionally, Time from Randomization to a loss of \geq 50% improvement on the YGTSS-TTS will also be analyzed using the following subgroups:

• Early Responders (at Week 4) and Later Responders (at Week 8)

The treatment of missing data and sensitivity analyses for the endpoints will be specified in the Statistical Analysis Plan.

13.4.2. Safety Analysis

All safety data will be summarized in Safety population according to the actual treatment.

Treatment-emergent adverse events (TEAEs) are defined as adverse events that are newly occurring or worsening after the first dose of study medication. The incidence of TEAEs will be summarized by treatment group, by severity and by relationship to study medication. Serious TEAEs and TEAEs leading to the study termination will be summarized by treatment group. Laboratory, vital signs, physical examination, and ECG data will be summarized by treatment and visit.

The Columbia-Suicide Severity Rating Scale (C-SSRS), the Children's Depression Rating Scale-Revised (CDRS-R), the Pediatric Anxiety Rating Scale (PARS), the Extrapyramidal Symptom Rating Scale (ESRS), the Swanson, Nolan, and Pelham (SNAP-IV-26) questionnaire, the Children's Yale-Brown Obsessive-Compulsive Scale-II (CY-BOCS-II), the Patient Health Questionnaire-9 (PHQ-9), the Hamilton Rating Scale for Anxiety (HAM-A), the Conners Adult ADHD Rating Scale Self Report: Short Version (CAARS-S:S) and the Yale-Brown Obsessive-Compulsive Scale-II (Y-BOCS-II) will also be summarized descriptively.

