12.1.12. Electrocardiogram (ECG)

Sites will be provided with a 12-lead ECG device to complete assessments per Table 3. Clinicians will instruct subjects to follow-up with care as appropriate upon evidence of new or worsening abnormal ECG readings.

12.1.13. Central Laboratory Tests:

Subjects should be in fasting state (minimum of 8 hours) for all blood laboratory tests collected at study visits after the Screening visit, per Table 3.

| Category | Test names |
|-------------------|--|
| Hematology | Red blood cell (RBC) count, hemoglobin (Hb), hematocrit (Hct), platelets, and white blood cell (WBC) count with differential (neutrophils, bands lymphocytes, monocytes, eosinophils, basophils, immature granulocyte) Mean Corpuscular Hemoglobin (MCH), Mean Corpuscular Hemoglobin Concentration (MCHC), Mean Corpuscular Volume (MCV), Mean Platelet Volume (MPV), Red Cell Distribution Width (RDW), CBC, Nucleated Red Blood Cell |
| Chemistry | Glucose, calcium, albumin, cholesterol, triglycerides, phosphorus, lactate dehydrogenase (LDH), total protein, globulin, prolactin; Liver function tests: albumin, alkaline phosphatase (ALP), aspartate aminotransferase (AST/SGOT), alanine aminotransferase (ALT/SGPT), total bilirubin, direct bilirubin, Calcium (Ca), Total cholest rol, glucose, lactate dehydrogenase (LDH), phosphorous, total protein, triglycerides; Electrolytes: sodium (Na), potassium (K), chloride (Cl), bicarbonate; Renal function tests: Blood urea/blood urea nitrogen (BUN), creatinine |
| Urinalysis | Complete urinalysis includes color, appearance, specific gravity, pH, protein, glucose, ketones, and blood with microscopic examination for positive protein or blood results |
| Pregnancy Test | A local urine test (for women of childbearing potential only) and central laboratory serum test to confirm a positive urine result |
| Urine Drug Screen | Central laboratory test to detect the presence of cocaine, amphetamine, benzodiazepines, barbiturates, phencyclidine (PCP), opiates |
| Special Test | Hemoglobin A1c (HbA1c) at Baseline, Week 12 and Week 24 |

| Emalex Biosciences, Inc. | Protocol EBS-101-TD-301 |
|--------------------------|----------------------------|
| Ecopipam | Version 9.0, 05 March 2024 |

Maximum blood volume to be drawn at each visit is noted below.

| Visit | Maximum Blood Volume (mL) |
|-----------------------------|---------------------------|
| Visit 1 – Screening | 6 |
| Visit 2 – Baseline | 8 |
| Visit 3 – Week 4 | 14 |

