# 8. General Aspects for Statistical Analysis

#### 8.1. General Methods

Study EBS-101-TD-301 is a multicenter global study. Investigative sites in the US are considered conducted under IND 109746 and non-US investigative sites are considered not conducted under IND 109746. Tables, Listings, and Figures will contain combined data from IND and non-IND investigative sites.

All analyses and outputs will be produced using SAS® version 9.4 or later. Unless otherwise specified, efficacy and safety summaries will be presented for each treatment. Continuous variables will be summarized using the number of observations (n), mean, standard deviation (SD), median, minimum, and maximum. Categorical variables will be summarized using number of observations (n), frequency, and percentages of subjects. Time-to-event variables will be summarized using Kaplan-Meier estimates of the 25th percentile, median and 75th percentile.

All relevant subject data will be included in listings. All subjects entered into the database will be included in subject data listings. All by-visit summaries will use the nominal visit. Unscheduled visits will not be summarized but will be included in the listings.

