#### 12.2. Laboratory Evaluations

Blood samples for hematology, chemistry, prolactin and urine samples for urinalysis are to be collected at screening, Baseline, Weeks 12 and 18, Completion [Week 24] or Relapse/Early Termination and 7 day and 14 day Follow Up visits. All results will be provided using International System of Units (SI). HbA1c will be measured at the baseline, week 12 and week 24 completion or early termination visits.

Descriptive statistics for hematology, chemistry, prolactin and HbA1c will be provided for each test parameter and for change from baseline treatment by visit and for each treatment group. Shift tables (i.e., low-normal-high at Baseline versus low-normal-high at each post-baseline visit in a 3-by-3 contingency table) will be provided for hematology, chemistry, prolactin, HbA1c and urine to assess changes from Baseline in laboratory values by visit for each treatment group. Shift (0.5% change) from baseline will be summarized for HbA1c by visit for each treatment group.

Separate listings will be provided for all laboratory evaluations (hematology, chemistry, prolactin, HbA1c and urinalysis.

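### For ALT, AST and bilirubin, SAP 12.2 has one undivided High category and no count of subjects by multiple of ULN, worst post-baseline value or concurrent rise

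*Protocol*

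**What the plan says.** The protocol collects the relevant tests. The chemistry panel in Protocol 12.1.13 includes "Liver function tests: albumin, alkaline phosphatase (ALP), aspartate aminotransferase (AST/SGOT), alanine aminotransferase (ALT/SGPT), total bilirubin, direct bilirubin". Protocol 13.4.2 says only that "Laboratory, vital signs, physical examination, and ECG data will be summarized by treatment and visit"; it names no category, grade or threshold.

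The operative text is SAP 12.2, which specifies four outputs:

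- **Summaries.** "Descriptive statistics for hematology, chemistry, prolactin and HbA1c will be provided for each test parameter and for change from baseline treatment by visit". SAP 8.1 defines their content: "Continuous variables will be summarized using the number of observations (n), mean, standard deviation (SD), median, minimum, and maximum".
- **Shift tables.** These set "low-normal-high at Baseline versus low-normal-high at each post-baseline visit in a 3-by-3 contingency table", for each treatment group.
- **One size-based table, for HbA1c.** "Shift (0.5% change) from baseline will be summarized for HbA1c by visit for each treatment group".
- **Listings.** "Separate listings will be provided for all laboratory evaluations".

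SAP 8.1 adds that unscheduled visits are listed but not summarised.

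**The concern.** Safety is a secondary objective (Protocol 6.2), and most of the planned enrolment is paediatric: about 196 children and adolescents and about 40 adults. For liver tests, a reviewer wants to know how many subjects had a large rise, in which period and arm, and whether transaminases and bilirubin rose in the same person. None of the planned laboratory tables is built to answer that. The categorical table records only whether a value is above the limit, not how far above. The continuous summaries describe a group at a visit, not a subject over time. Without prespecified bands, any later count would use cut-points chosen with the data in view.

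**Working it through.** The plan gives no figure to reproduce here. The check sets the relevant sections side by side and then uses a small illustration.

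**1. What each planned output shows for liver tests**

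| Output | Source | Size of rise? | Count of subjects by size? | ALT/AST and bilirubin in the same subject? |
|---|---|---|---|---|
| Descriptive statistics by visit | SAP 12.2, 8.1 | Only the extreme, through the maximum | No | No |
| 3-by-3 shift by visit | SAP 12.2 | No | No; above ULN or not | No |
| Listings | SAP 12.2 | Yes, per subject | No; reader must count | Only by hand |
| Adverse event tables | Protocol 12.2.1, 12.4; SAP 12.1 | Indirectly, by severity | Only for values recorded as events | No |

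**2. Illustration with assumed values.** Take one treatment arm of 49, the planned paediatric number per arm (SAP 4.3), and let one subject change. Arm mean change = (later value - baseline value) / 49, in units of ULN.

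| Baseline | Later | Shift-table entry | Arm mean change |
|---|---|---|---|
| 0.5 | 1.1 | Normal to High | (1.1 - 0.5)/49 = 0.012 |
| 0.5 | 3 | Normal to High | (3 - 0.5)/49 = 0.051 |
| 0.5 | 5 | Normal to High | (5 - 0.5)/49 = 0.092 |
| 0.5 | 10 | Normal to High | (10 - 0.5)/49 = 0.194 |
| 1.2 | 8 | High to High (no shift) | (8 - 1.2)/49 = 0.139 |

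The first four rows add the same single count to the same cell. The fifth sits on the diagonal. The mean moves by less than 0.2 x ULN throughout. The by-visit maximum would reveal the extreme if it fell at a summarised visit, but not whether one subject or several crossed a given level.

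**3. Timing.** After Baseline, the scheduled chemistry draws are Week 12, Week 18, Week 24/Relapse/ET and the two follow-up clinic visits (Protocol Table 3). A draw taken for cause between Baseline and Week 12 is therefore unscheduled, and SAP 8.1 leaves it out of the summaries. The windows in SAP 8.4 might bring some such results back, but SAP 8.1 says by-visit summaries use the nominal visit, so the text does not settle this. Even under the windows, a result is chosen mainly because it is the subject's last or lies closest to the target day. A peak followed by recovery can be passed over.

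**4. Reference point.** SAP 12.2 refers changes and shifts to Baseline only. Both randomised arms have already had 12 weeks of open-label ecopipam, so a shift from Baseline seen after Week 12 mixes open-label and post-randomisation change. SAP 8.2 already defines change from randomisation; SAP 12.2 does not use it.

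**5. Comparison within the SAP.** Size thresholds are set for ECG intervals (SAP 12.4, with bands for QTcF), for weight (7%, SAP 12.3) and for HbA1c (0.5%, SAP 12.2). None is set for ALT, AST or bilirubin. The list of special-interest events in SAP 16.5 names glucose, lipids, leukopenia/neutropenia and prolactin, but no liver test.

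**The case against.** A reader might infer that laboratory safety is tabulated only as means and shifts. The documents do not support that: the summaries also give SD, median, minimum and maximum, for value and for change, and HbA1c has its own size-based table.

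A reader might also infer that the plan cannot show an important liver change, or in which arm. That goes too far. Under Protocol 12.2.1 an abnormal result is an adverse event if it causes symptoms, needs intervention, interrupts or stops drug, or is judged clinically significant. Under Protocol 12.4, values that constitute a serious event or lead to stopping drug must be recorded. SAP 12.1 then counts subjects by treatment group, severity, relatedness, seriousness and termination. What remains is a rise that meets none of the mandatory triggers: whether it is recorded rests on the investigator's opinion. Protocol 12.4 grades intensity by tolerability and interference with activities, so a large but symptomless ALT rise could be recorded as mild. CTCAE grading in SAP 12.1 is for adverse events, where applicable, not for laboratory values as such.

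Three further points have weight. The High-to-High case should be uncommon, because Protocol 8.2 excludes hepatic impairment and clinically significant laboratory abnormalities at Screening. The 3-by-3 table does separate new High values from pre-existing ones. The earlier studies summarised in Protocol 5.2.2 and 5.3.1 report no laboratory concern. Since every value is listed, the tables could also be added at reporting. These points limit the urgency. They do not supply the missing counts, and tables added late would lack prespecified cut-points.

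**Conclusion.** The gap is real but narrow. For ALT, AST and bilirubin, SAP 12.2 does not separate small from large rises in its only categorical table, does not count a High-to-much-higher change as a shift, and specifies no count by multiple of ULN, by worst post-baseline value or by concurrent elevation. Adverse event tables and listings mitigate this only in part.

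The size cannot be put as a number of subjects, because the documents give no rate of liver-test abnormality; any figure for cases hidden in one High cell would rest on assumed rates. The values in the illustration are likewise assumed and show only how the tables behave. No efficacy test, alpha level or sample size is affected. This is an inexpensive improvement to descriptive safety reporting, in line with the thresholds the SAP already sets for ECG, weight and HbA1c.

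**What to change.** Keep the existing outputs and add to SAP 12.2:

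1. A per-subject table of the worst post-baseline value, including unscheduled results, in prespecified bands: for example ALT and AST at >=3, >=5 and >=10 x ULN, and bilirubin at >=2 x ULN.
2. A count of subjects with ALT or AST >=3 x ULN together with bilirubin >=2 x ULN, stating how close in time the two results must be.
3. Two presentations: open-label ecopipam for all treated subjects, and the randomised-withdrawal period by arm with Week 12 as reference. State whether follow-up draws count.

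These cut-points are a proposal for tabulation, not taken from the documents, and change no stopping or management rule. The sponsor may choose others, provided they are fixed before unblinding.

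Severity grading of neutrophils, glucose and lipids is optional. If CTCAE grades are used, the version must be reconciled: Protocol 7.5 and 8.3 cite version 5, and SAP 12.1 cites v4.03.

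The cost is a paragraph of SAP text and one or two programmed tables from data already collected, with no new samples. The downside is that the counts will probably be small and should be read as descriptive.
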